5.2 Clinical Experience

A phase 1 study has been performed at 5 sites in Germany, Italy and Switzerland. This was a dose escalation, multicenter study evaluating the safety, tolerability and pharmacokinetics of CetuGEX™ after intravenous administration in patients with locally advanced and/or metastatic solid cancers. The effect of CetuGEX™ on the development of anti-drug antibodies and on tumor response was also evaluated. This was an open-label, dose-escalation study in a 3 + 3 design, in which 3 to 6 eligible patients were enrolled into each of the sequential ascending dosing cohorts. CetuGEX™ was administered in 500 ml physiologic saline solution by intravenous infusion over a 2 or 3 hour-period, later amended to a more complex scheme.

Until the relevant cut-off date for the clinical study report, 40 patients were treated on a weekly (8 dose levels from 12 to 1370 mg flat dose), or once-every-two-weeks (990 mg flat) schedule. Twenty-four patients had received at least 8 weekly doses and were thus evaluable for activity. The most frequently observed related treatment-emergent adverse events (TEAEs), all grades, apart from infusion related reactions (IRRs), were acneiform dermatitis (25%), skin rash (28%), asthenia (15%), fatigue (13%) and nausea (10%). Observed IRRs, all grades, (70%), virtually restricted to the first infusion and most of mild or moderate grade, were associated with cytokine secretion: IL-6, IL-8, TNF α , IFN γ and IP-10 as marker of macrophage activation. An optimized infusion scheme and premedication reduced the incidence of IRRs. Activity was seen over all dose levels. One patient with non-small cell lung cancer achieved a complete response. Another 2 patients with esophageal and gastric cancer without measurable disease at study entry had marked improvement of symptoms and normalization of tumor markers. Additional 15 patients had stable disease lasting from 8 weeks to over a year, including several minor responses, leading to a clinical benefit rate of 45% (18/40) in the overall and 75% (18/24) in the PP population. Pharmacokinetics (PK) supports weekly and bi-weekly dosing. One additional patient was included into the study after the cut-off date and results of this patient are not yet included within the summary presented above.

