During the combination treatment phase, all randomized patients will receive 5-FU as continuous intravenous infusion, in combination with cisplatin (or carboplatin in case of required substitution of cisplatin in further cycles). This platinum-based chemotherapy will be administered for a maximum of 6 cycles of 3 weeks each, starting approximately 1 hour after CetuGEX™/cetuximab infusion on Day 1 of each cycle. If the CetuGEX™/cetuximab infusion is administered in the afternoon, the concomitant

platinum-based chemotherapy may be administered the next morning; however, all drugs should be given within 24 hours.

5-fluorouracil will be administered in doses of 1000 mg/m² BSA per day every 3 weeks (one cycle of cisplatin or carboplatin treatment) as continuous intravenous infusion on Days 1 to 4 of each cycle.

Cisplatin will be administered as a dose of 100 mg/m² BSA by infusion every 3 weeks, on Day 1 of each cycle, according to current standards and prescribing guidelines including hydration before and after cisplatin treatment, as required (please refer to the instructions in the corresponding SmPC [Appendix F]). In case cisplatin has to be replaced by carboplatin for toxicity reasons, Carboplatin will be administered at an area under the curve (AUC) of 5 mg/mL/min (using the Calvert formula for calculation¹²) as a 1-hour intravenous infusion every 3 weeks, on Day 1 of each cycle. As per SmPC (Appendix H), carboplatin may not be used in patients with bleeding tumors.

In case of related relevant toxicity, each compound of the chemotherapy treatment can be discontinued prior to completion of 6 cycles of chemotherapy, and patients will continue with the remaining compounds of the combination therapy. After all chemotherapy has been discontinued, irrespective if the 6 cycles are completed or discontinued prematurely for any other reason apart from progression, patients will directly enter the maintenance phase.

Single-Agent Maintenance Treatment Phase

After completion or discontinuation of chemotherapy for any other reason apart from progression, the treatment will be followed by maintenance therapy receiving CetuGEX™ alone or cetuximab alone, respectively. Single-agent maintenance therapy will be continued with unchanged dosing schedule until progression of disease or limiting toxicity.

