### **10.1 Adverse Events**

Adverse Events will be coded using MedDRA version 16 or newer.

An AE is defined as treatment emergent (TEAE), if the first onset or worsening is at or after the first administration of IMP (CetuGEXTM or cetuximab) and within 28 days after last administration.

If the start date or time of an AE is partially or completely missing, the AE will be assumed to be treatment-emergent if it cannot be definitely shown that the AE did not occur or worsen during the treatment emergent period (worst case approach). Missing dates and times will not be replaced for display in listings and further calculations.

Thus, the following approach will be taken:

- If the start time of an AE is missing, but the start date is complete, an AE will only be excluded from treatment-emergent AEs if the start day is before day of first treatment or the start day is after end day of the treatment-emergent period.
- If the start time and day are missing but the start month is complete, an AE will only be excluded from treatment emergent AEs if the start month is before month of first treatment or the start month is after end month of treatment-emergent period or if the stop date/time information is sufficient to show the event ended before the start of treatment.
- If the start day and months are missing but the start year is complete, an AE will only be excluded from treatment-emergent AEs if the start year is before year of first treatment or if the start year is after end year of treatment-emergent period or if the stop date/time information is sufficient to show the event ended before the start of treatment.
- If start date is completely missing, an AE will not be excluded from treatment-emergent AEs unless the stop date/time information is sufficient to show the event ended before the start of treatment.

Time from first treatment to onset of AEs [days] and duration of AEs [days] will be calculated for complete dates only and will be included in listings.

In the following infusion related reactions (IRRs) are defined as AE marked as infusion related reactions (IRRs) by the investigator and/or specific AEs which occurred at or the day after an infusion. The relevant AEs will be identified as a list of Preferred Terms which will be compiled before data base lock.

An AE summary table will be presented including rows with the number of patients with

- AEs
- TEAEs
- SAEs

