- Any Deaths (NCI CTCAE V4.0 Grade 5 TEAEs and/or with an outcome of death)
- NCI CTCAE Grade 4, 3, 2, 1 TEAEs
- Adverse drug reactions (ADRs) (related or possibly related TEAEs)
- TEAEs leading to withdrawal of study treatment

- TEAEs leading to drug interruption or infusion rate reduction
- TEAEs requiring additional medication
- TEAEs constituting IRRs
- TEAEs marked as disease related symptoms

Incidences of TEAEs will be presented for all TEAEs and separately for the combination treatment (TEAE which occurred before first maintenance treatment) and maintenance treatment (TEAE which occurred at or after first maintenance treatment).

Incidences of TEAEs will be calculated on Preferred Term level, on System Organ Class level (SOC) and globally by treatment group. On each analysis level, a patient will be counted only once. Summaries of incidence rates (frequencies and percentages) of individual TEAEs by MedDRA SOC and Preferred Term will be prepared. Such summaries will be displayed for all TEAEs, TEAEs by maximum severity graded according to NCI-CTCAE (Version 4.03), TEAEs by strongest relationship to study treatment, and TEAEs by strongest relationship to chemotherapy. In the SOC/PT tables, events with missing grade or relationship information will be classified into the worst category. No statistical tests will be performed. In addition, separate summaries of incidence rates of IRRs and all TEAEs without IRRs by SOC and PT will be given.

IRRs will be linked to the last infusion administered before the occurrence of the IRR. Incidence rates will be calculated by SOC and PT on a per infusion basis. Moreover the first infusion per patient with a least one IRR will be identified and summarized in frequency tables.

Also, a summary of incidence rates of TEAEs by SOC and PT and of incidence rates of IRRs by FcγRIIIa-allotype subgroups (FF, FV and VV), by FcγRIIa allotypes (HH, HR, RR) the occurrence of ADAs (no/yes) and the CetuGEX™ concentration ( $C_{max}$ ) after the 3rd infusion ( $\leq$  median/ $>$ median) will be prepared.

In the AE listings all recorded AEs will be included, TEAEs will be identified by a flag variable.

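### The planned per-infusion IRR rate has no stated denominator; if all infusions are pooled, the arm treated longer looks less reactive at equal first-infusion risk

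*SAP*

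**What the plan says.** SAP 10.1 attributes each reaction to an infusion: "IRRs will be linked to the last infusion administered before the occurrence of the IRR". It continues: "Incidence rates will be calculated by SOC and PT on a per infusion basis". No denominator is given, and no breakdown by infusion number is mentioned. The table list in SAP 15.1 has one table for this rate, numbered 14.3.1.5.3.

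Two other IRR summaries are planned in the same section. One is per patient: "separate summaries of incidence rates of IRRs and all TEAEs without IRRs by SOC and PT will be given", with each patient counted once at each level. The other is by first occurrence: "Moreover the first infusion per patient with a least one IRR will be identified and summarized in frequency tables"; in the table list it is also numbered 14.3.1.5.3. On the adverse event tables the SAP adds: "No statistical tests will be performed".

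An IRR is an event marked as such by the investigator and/or one of the "specific AEs which occurred at or the day after an infusion", taken from a list of preferred terms to be compiled before database lock.

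On timing, Protocol 5.2 reports phase 1 IRRs in 70% of CetuGEX patients, "virtually restricted to the first infusion". Protocol 9.9 says mild or moderate IRRs occur mainly with the first infusion of either antibody. Protocol 9.9.2 says severe cetuximab reactions usually come with the initial infusion but can come hours later or with subsequent infusions. Under Protocol 9.3 both antibodies are given weekly until progression or limiting toxicity.

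**The concern.** A per-infusion rate compares arms fairly only if the risk is roughly constant across infusions, or if both arms have the same mix of early and late infusions. Neither is expected here. The risk is concentrated at infusion 1, and the number of later infusions is set largely by time to progression, which the trial expects to be longer on CetuGEX. The more effective antibody would then show the lower IRR rate even with an identical first-infusion risk.

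IRRs are a named safety endpoint and were very common with CetuGEX in phase 1. A reader who takes the per-infusion table as a comparison of arms could conclude that CetuGEX is better tolerated, or could overlook an excess.

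A second, smaller issue is the preferred-term rule. On Day 1 of each cycle the antibody is followed by chemotherapy: "This platinum-based chemotherapy will be administered for a maximum of 6 cycles of 3 weeks each, starting approximately 1 hour after" the antibody infusion. A listed term caused by chemotherapy on Day 1 or Day 2 would be counted as an IRR. Because of the split first dose, the rule covers Days 0 to 2 for CetuGEX and Days 1 to 2 for cetuximab.

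**Working it through.** **Inputs from the documents.** Median PFS 5.6 and 8.4 months, 240 patients randomized 1:1, 192 events, two-sided 0.05, 80% power, 10% drop-out at the cut-off (Protocol 13.2, SAP 5). Accrual 24 months plus 12 months of follow-up to the main analysis (Protocol 13). Weekly dosing (Protocol 9.3). IRRs in 70% of phase 1 CetuGEX patients (Protocol 5.2).

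**Assumptions not in the documents.** Exponential time to progression; in the base case, treatment stops only at progression or the cut-off; the same 70% first-infusion risk on cetuximab; the later-infusion risks and discontinuation rates used below.

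**Check of the plan's own figure.** The Schoenfeld formula gives 191 events at a hazard ratio of 5.6/8.4 = 0.667 and 196 at 0.67. With uniform accrual and exponential drop-out set to 10%, 240 patients yield about 194 events at 36 months. The stated 192 is reproduced, so these medians are a fair basis for expected treatment length.

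**Infusions per patient.** The monthly progression hazard is ln 2/median: 0.1238 (cetuximab) and 0.0825 (CetuGEX). With 30.4375/7 = 4.348 weeks per month, the probability of going on to the next infusion is r = exp(−hazard/4.348) = 0.972 and 0.981.

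- Without a cut-off, mean infusions = 1/(1 − r) = 35.6 and 53.2.
- With the cut-off, a patient entering at month a can receive at most K infusions, K being the whole number of weeks in (36 − a) months, plus 1. Averaging (1 − r^K)/(1 − r) over a from 0 to 24 gives m = 33.1 and 44.7.

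**Pooled rate.** Rate = [p1 + q(m − 1)]/m, where p1 is the risk at infusion 1 and q the risk at each later infusion.

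| Case (p1 = 70% in both arms) | Cetuximab | CetuGEX | Ratio |
|---|---|---|---|
| q = 0, 36-month cut-off | 0.70/33.1 = 2.12% | 0.70/44.7 = 1.57% | 0.74 |
| q = 0, no cut-off | 0.70/35.6 = 1.96% | 0.70/53.2 = 1.32% | 0.67 |
| q = 0.5%, cut-off | 2.60% | 2.06% | 0.79 |
| q = 2%, cut-off | 4.05% | 3.52% | 0.87 |
| q = 0, other discontinuation 3% per month, cut-off | 2.54% | 1.96% | 0.77 |
| q = 0, other discontinuation 10% per month, cut-off | 3.56% | 2.95% | 0.83 |
| q = 0, cut-off, split dose counted as two infusions | 2.12% | 0.70/45.7 = 1.53% | 0.72 |

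With later risk and other discontinuation together, over the same values, the ratio is 0.81 to 0.89.

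**Masking.** In the base case with the cut-off, pooled rates are equal when the cetuximab first-infusion risk is 0.70 × 33.1/44.7 = 52% and the CetuGEX risk is 70%.

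**By infusion number.** With patients who received infusion 1 as the denominator for infusion 1, equal risk reads 70% against 70%, whatever the treatment length.

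**The case against.** The strongest reply is that the neighbouring tables already answer the question. At equal risk with no later IRRs, the per-patient table shows 70% in each arm, and the first-occurrence table places the events at infusion 1. No tests are done, and the number of infusions is tabulated under exposure. This largely stands. A reader might infer that the SAP would hide a real CetuGEX excess, but that would require ignoring the two tables beside the per-infusion one.

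The neighbours are not a complete substitute. If later IRRs occur, per-patient incidence leans the other way: at 70% first and 2% later in both arms, with the cut-off, it is 82% for cetuximab and 85% for CetuGEX, because longer treatment gives more chances. The two tables could then point in opposite directions. The first-occurrence table leaves out repeat reactions and has no stated at-risk denominators.

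Second, pooling is inferred. A reader might say the SAP divides by all infusions given; it does not say so, and linking each IRR to an infusion would permit a breakdown.

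Third, almost no IRRs after infusion 1 is a phase 1 CetuGEX finding. Protocol 9.9.2 allows later reactions on cetuximab, and the SAP's own preferred-term rule may add later events. Both shrink the distortion, so 0.67 is an extreme rather than an expected value. The documents give no cetuximab IRR rate.

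Fourth, a reader might infer that chemotherapy events on Days 1 and 2 become IRRs wholesale. Only terms on a list still to be compiled qualify, and chemotherapy starts alongside at most six infusions. The rule can capture such events; how many is unknown.

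**Conclusion.** The point holds in a limited form. SAP 10.1 leaves the per-infusion denominator undefined. On the natural pooled reading, the table favours the arm treated longer whenever IRR risk is front-loaded. The size is a ratio of about 0.74 at truly equal first-infusion risk in the base case, and about 0.77 to 0.87 with either modest later risk or other discontinuation. These figures rest on the planning medians, exponential progression and an assumed equal 70% first-infusion risk; if treatment lengths turn out equal, the ratio is 1. One descriptive table is affected, and no confirmatory conclusion depends on it. The change is worth making because a table without this distortion needs only what the SAP already derives.

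**What to change.** In SAP 10.1 and the per-infusion table shell:

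- Replace the pooled rate by IRR incidence by infusion number (1, 2, 3, 4 and later), with patients who received that infusion as the denominator. The last row still grows with time on treatment, so label it as such.
- State that Day 0 plus Day 1 counts as infusion 1 for CetuGEX, as Protocol Table 9-1 already groups them.
- State that arms will not be compared on a pooled per-infusion rate.
- Tabulate investigator-marked IRRs separately from those added only by the preferred-term and day rule.
- Give the per-infusion and first-occurrence tables different numbers.

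Ending the preferred-term window at the start of chemotherapy may look attractive, but it should not be done. It would cut cetuximab's first-infusion window to about one hour after the infusion, while CetuGEX Day 0, which has no chemotherapy, would be left uncut. It would also lose the delayed reactions described in Protocol 9.9.2. And it needs chemotherapy start times, whereas the infusion times listed for recording in Protocol 9.3 are for the antibodies only.

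The cost is SAP wording, revised shells and slightly more tabulation. IRRs are already to be linked to infusions, so no new data are needed.

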### **10.1.3 Adverse Events of Special Interest**

The times to the first occurrence of neutropenia (CTC-grade  $\geq 3$ ), liver enzymes increases (CTC-grade  $\geq 3$ ), (hypomagnesemia (CTC-grade  $\geq 3$ ), skin reactions (SOC="Skin and subcutaneous tissue disorders"), gastrointestinal symptoms (SOC="Gastrointestinal disorders), mucositis (PT="Mucositis") and conjunctivitis (PT="Conjunctivitis") will be investigated by Kaplan-Meier methods. Patients who did not experience this AE will be censored at the Safety Follow-up visit.

Logistic regression models including the CetuGex plasma concentration after the 3rd infusion as continuous covariable will be fitted to the incidences of AEs of special interest. Separate analyses will be performed for each of the AEs. Odds ratios, the corresponding 95%-confidence intervals and the p-values of the Wald test will be presented. Moreover, sample statistics of the CetuGex plasma concentration after the 3rd infusion grouped by the occurrence of these AEs (yes/no) will be presented including p-values of the Wilcoxon rank test.

AEs of special interest will be omitted from these analyses if their overall incidence is < 5%.

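### SAP 10.1 groups infusion-related reactions by a CetuGEX level drawn about two weeks after most of them are expected; SAP 10.1.3 has the same ordering for AEs of special interest, with probably small bias

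*SAP*

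**What the plan says.** SAP 10.1 treats an adverse event as treatment-emergent "if the first onset or worsening is at or after the first administration of IMP", up to 28 days after the last dose. It then plans "Also, a summary of incidence rates of TEAEs by SOC and PT and of incidence rates of IRRs by" receptor allotype, "the occurrence of ADAs (no/yes) and the CetuGEX™ concentration" (Cmax) after the third infusion, the last split at the median. For the tables by system organ class and preferred term the section states "No statistical tests will be performed". A separate per-infusion summary is planned, for which "IRRs will be linked to the last infusion administered before the occurrence of the IRR".

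SAP 10.1.3 goes further. "Logistic regression models including the CetuGex plasma concentration after the" third infusion are to be fitted to the incidence of each AESI, with Wald p-values and a Wilcoxon comparison of levels by event status. It adds that "AEs of special interest will be omitted from these analyses if their overall incidence is" below 5%. IRRs are not among the seven AESIs.

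Neither section restricts onset to the time after the sample or sets a landmark. Table 14.3.1.6.4 (SAP 15.1) covers TEAEs by third-infusion concentration. No listed table covers IRRs by concentration, although the text of 10.1 promises one.

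On timing, Protocol 9.3 (Table 9-1) puts infusion 1 on Days 0 and 1, infusion 2 on Day 8 and infusion 3 on Day 15. Protocol 5.2 says phase 1 IRRs (70% of patients) were almost all at the first infusion, and Protocol 9.9 expects the same pattern here.

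**The concern.** An exposure-response summary is read as relating events to the exposure that produced them. Here a Day 0 or Day 1 reaction is sorted by a concentration drawn 14 to 15 days later. Patients with a grade 3 or 4 reaction at infusion 1 or 2 must stop CetuGEX (Protocol 9.9.1, Table 9-2). They never have the level, so the most severe early reactors drop out of the table meant to relate reactions to exposure. A reader could draw a wrong conclusion in either direction about whether higher levels carry more reactions.

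For the AESIs, the worry is that an early event may change later dosing and so lower the level used to explain it. The relation of PK to safety is a safety variable in SAP 2.2.2 but not a safety endpoint in Protocol 13.1.4. What is at stake is therefore a supportive safety statement, not the trial's main result.

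**Working it through.** The plan gives no figure of its own for this comparison, so there is none to reproduce.

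**1. Time order of IRRs**
- About 240 patients randomised 1:1 gives about 120 on CetuGEX (SAP 5).
- IRR incidence: 70% in phase 1, later reduced by a better infusion scheme and premedication (Protocol 5.2); 30% is an assumed lower bound. Patients with an IRR: 0.30 × 120 = 36 to 0.70 × 120 = 84.
- Share at infusion 1: 80–95% (assumed, in line with the protocol's description). IRR at infusion 1: 0.80 × 36 = 29 to 0.95 × 84 = 80. First IRR at infusion 2 or later: 0.05 × 36 = 1.8 to 0.20 × 84 = 16.8, so 2 to 17.
- Even if only 60% of 84 first IRRs fell at infusions 1–2, that is 50 of 84, still a majority.

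**2. Patients without a level**
- If 0–5% are withdrawn before infusion 3 (assumed): 0 to 0.05 × 120 = 6.
- Protocol 5.3 reports a few grade 3 IRRs in phase 1, whereas Protocol 9.9.1 reports no severe ones. The two statements must be reconciled, because they bear on this count.

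**3. Does time order alone bias the comparison?**
Null simulation in which level has no effect on events: 120 patients, early events in 0.7 × 0.9 = 63%, 5% of those withdrawn, later events in 10%, log-SD of level 0.3, half-life 3–7 days (all assumed). High-versus-low odds ratio:
- no infusion skipped: 0.98–1.02;
- infusion 2 skipped by 10% of early-event patients: 0.87–0.92; by 30%: 0.65–0.78;
- events after infusion 3 only: 0.99–1.02.

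Withdrawals unrelated to the level do not move the odds ratio. Feedback from event to dosing does.

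**4. Where the documents allow such feedback**
Protocol 9.9 limits CetuGEX dose adjustment to related grade 3 skin toxicity and does not allow withholding for chemotherapy-related toxicity. Protocol 9.9.1 allows up to two consecutive infusions to be skipped for grade 3 skin toxicity. That is a route for one of the seven AESIs.

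Size of the level change (one compartment, bolus doses of 990 mg then 720 mg weekly, half-life 3–10 days assumed), for the third infusion actually given. Example at half-life 7 days:
- no skip: 720 + 360 + 247.5 = 1327.5;
- Day 15 skipped: 720 + 180 + 123.75 = 1023.75, ratio 0.771, a drop of 22.9%.

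Over the half-life range the drop is 3–9% if Day 8 is skipped and 16–23% if Day 15 is skipped.

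**5. Effect on the skin-reaction Wilcoxon test**
Null simulation: 120 patients, 4000 runs per setting, level CV 25% or 40%, drop 8% or 22%, all skips placed in patients with the event. False-positive rate at nominal 5%:

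| Patients skipping | Incidence 30% | Incidence 60–85% |
|---|---|---|
| 2–5% | 4.8–10.5% | 4.5–6.8% |
| 10% | 6.2–33.6% | 4.8–12.7% |

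With no skips the rate is 4.4–5.3%. The 33.6% needs 12 of 36 skin-reaction patients, one third, to skip before infusion 3.

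**The case against.** The best defence is that dosing is flat, so a Day 15 level may stand in for a patient's earlier exposure. Step 3 supports this: without dosing feedback the comparison stays centred on no effect. That disposes of a stronger reading, that every PK-safety output is biased because the sample is late. The documents do not support it, and they show no dosing feedback for the other six AESIs.

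A reader might also infer that a significance test on IRRs is invalid. None is planned: the IRR split in 10.1 is descriptive, and p-values arise only in 10.1.3, which excludes IRRs. IRR timing is also shown in the per-infusion and first-occurrence tables, so a careful reader would see the clustering.

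Nor is the number without a level hidden. SAP 7.1 and 13.2 require counts of non-missing values, and 10.1.3 asks for sample statistics of this concentration, so it can largely be found by subtraction. What is missing is the reason, set beside the table.

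The level drops in step 4 assume the third infusion given. If Day 15 is meant, a patient who skips it has only a pre-dose sample (Protocol 10.1.3, Appendix B), and the level is missing rather than lowered. SAP 10.1.3 does not say which is meant, and SAP 9.3.3 uses the same phrase for both the trough and the post-infusion level.

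What remains after these points is the IRR breakdown. Proxy or not, it groups mostly first-infusion events by a later level and leaves out early severe reactors.

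**Conclusion.** The point holds for the IRR-by-Cmax summary in SAP 10.1, which cannot support an exposure-reaction reading. For the AESI models in 10.1.3 the ordering is the same but the consequence is limited. With 2–5% of patients skipping an early infusion and a skin-reaction incidence of 60–85%, the test runs at 4.5–6.8% against a nominal 5%. It becomes material only if early skips are frequent or skin reactions less common. The IRR shares, half-life, variability, and skip and withdrawal rates are assumptions, so the actual size of any bias is unknown. Severity is minor to moderate: the outputs are supportive and the primary PFS test is untouched.

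**What to change.** 1. **SAP 10.1, IRRs.** Do not break down IRRs at infusions 1–3 by third-infusion Cmax. Use the planned link between each IRR and its infusion to restrict that breakdown to later infusions, or delete it. Align the table list in SAP 15.1 with the choice.
2. **SAP 10.1.3.** State that the covariable is the end-of-infusion level of the third infusion given. Keep the planned models, labelled as associations. Add a landmark sensitivity run, at least for skin reactions, counting only first onsets after that sample among CetuGEX patients who have a level and are free of that AESI at that time.
3. **Table 14.3.1.6.4.** Keep it as a descriptive association. If it is landmarked, each row's denominator must exclude patients who already had that event. Otherwise they count as non-events and the table can reverse. For example, take early events in 60% (high level) versus 30% (low), and later events in 50% versus 40% of the rest. True incidence is 0.60 + 0.40 × 0.50 = 80% versus 0.30 + 0.70 × 0.40 = 58%, but the table would show 0.40 × 0.50 = 20% versus 0.70 × 0.40 = 28%.
4. **Footnote** the number of CetuGEX patients without a third-infusion level, and why.

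The cost is SAP wording and programming. The samples (Protocol 10.3.3.1), AE start times (Protocol 11.2.3) and IRR link are already planned, and SAP 9.3.1 already uses an at-risk landmark. There is no need to replace every TEAE and AESI analysis with a landmarked one.

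The landmark run will have few events. An AESI with 5–20% incidence (6–24 of 120) keeps about 1–19 if 20–80% of events come before the sample (assumed), so some models may fall below 5% (6 of 120). Its results apply only to later events in patients who tolerated the first infusions.
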